The purpose of this study is twofold: (1) to assess the impact a mobile health tool may have on reducing alcohol use and improving quality of life for patients with moderate to high risk drinking patterns and/or mild to moderate alcohol use disorder; and (2) describe how mobile health technology designed to support alcohol use reduction may be effectively integrated into primary care.

The primary aim of this study is to assess the impact on risky drinking patterns and quality of life for patients with risky drinking patterns or mild to moderate alcohol use disorder among patients who self-refer to our study from a primary healthcare system. Patients in the trial will be given versions of an evidence-based mobile-health (mHealth) system (A-CHESS) that is delivered using different implementation strategies according to study group. The original A-CHESS is an evidence-based, smartphone-delivered system characterized by the essential elements of relapse prevention: long duration,^{1,2} assertive outreach,³ monitoring,⁴⁻⁶ prompts,⁷⁻⁹ case management,¹⁰⁻¹² and peer¹³⁻¹⁵ and family¹⁶⁻¹⁸ support that was tested among patients exiting 90-day residential treatment for severe alcohol use disorder. A-CHESS has more than 18 services designed to improve social relatedness (e.g., online peer discussions), coping competence (e.g., guided relaxation and other interventions), and intrinsic motivation (e.g., reminders of why a patient wants and needs to control his or her drinking).

The version of A-CHESS to be tested in this trial maintains its core components but is modified to be appropriate for a self-referred study population in a primary healthcare system who are likely to represent a broad spectrum of patients who use alcohol. We have named this modified version of A-CHESS “Tula,” from the Sanskrit word for balance. We propose to randomly assign 546 patients who self-report moderate- to high-risk drinking patterns from UW Health clinics to one of 3 groups: 1). A self-monitoring group that receives information on alcohol, 2). A peer-supported group that uses the Tula system independently of the health system, or 3). A version of the Tula system that is clinically integrated in the health system.

Secondarily, we want to detect differences between groups in health system use, whether patients’ sex (male/female) moderates outcomes, whether effects are mediated by measures of competence, relatedness, and autonomous motivation, and whether levels of use of Tula correlate to changes observed in health outcomes (i.e., dose/response relationship). The study is designed to isolate and examine the role of the clinician in delivering an mHealth system. The cost-effectiveness of each approach will be assessed. This research examines a unique and promising mHealth system with potential clinical, economic, and societal importance and aims to determine the most cost-effective strategy for implementing mHealth into primary healthcare systems.

Protocol
HS IRB #2019-0337
Version 5. 10/17/19
Version 6. 04/07/20
Version 7. 10/09/20
Version 8. 01/26/21
Version 9. 08/18/21
Version 10. 07/13/23

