1. In the first large randomized trial⁵⁰ studying the effects of mHealth on alcohol use disorders (AUDs), patients (n=349; 39% women) leaving residential treatment were randomly assigned to A-CHESS or usual care for 8 months and followed for 12 months. Over this period, those with A-CHESS had 57% fewer risky drinking days than those without it as well as longer abstinence. Participants used A-CHESS heavily, with nearly 60% still using it at 8 months.
2. In the most recent implementation research trial⁵¹ which studied the effects of mHealth patients with a range of substance use disorders (n=268; 48% women) in federally qualified health centers (primary care clinics that serve patients regardless of their ability to pay) were provided access to an iteration of A-CHESS, called Seva, for 12 months. Over this period, patients had a 44% reduction in risky drinking days and improvements in self-reported quality of life. Patients sustained heavy use of the system over the 12 months across the three clinics. This suggests that Tula (the version of A-CHESS central to this study; see description, below) may prove to be an effective tool to reduce alcohol consumption in primary care patients.

Tula is a mobile health system based on A-CHESS but modified for self-referred patients in primary care who want to reduce their drinking. Participants are likely to represent a wide spectrum of patients, from those concerned about their drinking to those whose lives are seriously affected by their drinking. Patients randomized to all three groups in the study will download Tula on their smartphones and receive the same static content. This static content will appear in the following sections:

Thought of the Day—an inspirational quote intended to motivate participants.

Motivation—Participants can record, in words and photos, their reasons for wanting to work on their drinking and wellness; respond to a prompt to write a daily reflection; complete or revise What Matters to Me, about why they want to work on their drinking and wellness; and save favorites in Tula.

Tracker—Participants can set goals for 90 days—how many total drinks they'll have in a week and the number of days per week they'll be drinking as well as goals related to other aspects of

Protocol

HS IRB #2019-0337
Version 5. 10/17/19
Version 6. 04/07/20
Version 7. 10/09/20
Version 8. 01/26/21
Version 9. 08/18/21
Version 10. 07/13/23

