wellness, such as exercise and sleep; keep track of their progress week by week; and take the weekly survey about factors related to drinking and wellness (mood, sleep, social pressure, etc.)

Information—Participants will see a library of information related to wellness, such as building healthy habits, reducing drinking, food and nutrition, physical activity, etc.

Relaxation—Information on relaxation techniques and audio recordings for meditation and binaural beats.

Strategies—Tips for reducing drinking and meeting other health goals, including “Rethinking Drinking” from National Institute for Alcohol and Alcohol Abuse, cognitive behavioral therapy, and quick tips for building skills related to making changes.

The content of Tula will vary by randomization group in two ways: the in-app communication services participants can access, and whether they work with a health coach, as follows:

- In the self-monitoring group, participants will not have access to a discussion group with others using the app. They will be able to send private messages only to the research coordinator (a member of the research team).
- In the peer-supported group, participants will have access to a discussion group available to all members of the group and moderated by a trained peer specialist. Participants will identify themselves in the discussion group by usernames they create, not by their real names. Participants in this group will be able to send private messages to others in the peer-supported group as well as to the peer moderator. If participants have a question that the peer moderator cannot answer, he or she will refer the question to the research team.
- In the clinically integrated group, participants will have access to a discussion group available to all members of the group and moderated by a health coach. Participants will identify themselves in the discussion group by usernames they create, not by their real names. In addition, patients can send private messages to other members of the clinically integrated group and to the health coach. If participants have a question that the health coach cannot answer, he or she will refer the question to the research team. Participants in this group will be encouraged to have up to three sessions in person or by phone with the health coach at the beginning, middle, and end of the active 90-day implementation period.

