2.0 STUDY OBJECTIVES

This project proposes a hybrid type II effectiveness/implementation trial that will test the effect on risky drinking patterns and quality of life associated with patient use of an mHealth system under a variety of implementation

Primary Aim:

Detect the effectiveness of interventions by assessing the difference in self-reported risky drinking patterns and quality of life between subjects in the three study groups (self-monitoring, peer-supported, and clinically integrated groups).

Secondary Aims:

Because the study is designed to investigate both the effectiveness of Tula in primary care and the comparative effectiveness of different implementation strategies, the following secondary goals complement study's primary aims:

- Understand the significance clinician monitoring has on alcohol use interventions and patient outcomes.
- Calculate the costs of health system use for each group.
- Develop an mHealth reimbursement strategy prototype using CMS billing codes in the clinically integrated group.
- Understand the degree to which sex moderates the intervention outcomes among Tula users.
- Understand the degree to which patient competence, relatedness, and autonomous motivation (three tenets of self-determination theory) mediate the intervention effect in the Tula groups.
- Assess the dose/response relationship between Tula use and degrees of outcomes
- Understand the impact clinician monitoring has on AUD treatment.
- Qualitatively assesses clinician engagement and clinic needs to further refine Tula and its associated integration for future implementation and dissemination.

Sub-aim:

- Understand the relationship between pain and alcohol consumption after the 3-month active intervention.

Study Coordination

The Implementation Science and Engineering Lab is the coordinating site for this study. The UW study coordinator will oversee all activities at participating UW Health recruitment sites. Activities include:

- developing site-specific recruitment and data collection processes that meet study objectives;
- training the health coaches on protocol procedures prior to the start of recruitment and continuous monitoring to assure compliance with the protocol and human subjects regulation;
- communicating with site staff via regular conference calls to monitor progress, inform of protocol

Protocol

HS IRB #2019-0337
Version 5. 10/17/19
Version 6. 04/07/20
Version 7. 10/09/20
Version 8. 01/26/21
Version 9. 08/18/21

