Peer-supported group. In addition to the static content available to patient subjects in all three groups, patient subjects in this group will have access to a discussion group where they can message one another and have the ability to share and see posts of other patients. The only involvement of someone other than patients themselves in the peer-supported Tula group will be by a trained peer mentor (i.e., a dedicated Tula user from the area with a sustained history of successful alcohol reduction). The peer mentor will participate in Tula discussion groups, moderate the discussions, and encourage use of the system (e.g., by posting topics in the discussion group, pointing Tula users to a potentially helpful tip). The peer mentor will not have access to individual Tula use data. Patient-reported feedback will be presented directly to the patient only. The peer mentor will be introduced to

Protocol

HS IRB #2019-0337
Version 5. 10/17/19
Version 6. 04/07/20
Version 7. 10/09/20
Version 8. 01/26/21
Version 9. 08/18/21
Version 10. 07/13/23

the study by the study coordinator and receive access to Tula for 36 months.

Two Certified Peer Specialists from Safe Communities of Madison-Dane County will provide participant mentoring and discussion forum moderation for the peer-supported group. These peer specialists, who will serve as peer mentors for the study intervention, completed the CITI Human Subjects Research Training: UW Biomedical Course using the materials and attestation form provided by UW's Human Research Protection Program (HRPP) and have been added to the IRB study record as external personnel.

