Clinically integrated group. In addition to receiving the same static content available to all patients, patients in the clinically integrated group will also have access to a discussion group with others in the group (like the peer-supported group described above) and access to a health coach from the UW Health Wellness Center. Health Coaching at UW Health's Center for Wellness at the American Center is provided by a Certified Wellcoach, either in-person at the American Center or over the phone. Health Coaching sessions are not scheduled via Health Link: Health Coaches directly and independently manage their own client calendars. Patients schedule a session directly with the Health Coach via phone or email. When the Health Coach sees a client for more than one session, they schedule the first session via phone or email, then set up subsequent sessions during the first session. Standard clinical Health Coach appointments are not documented in any way in Health Link, nor will they be for this study; as an out-of-pocket, open-to-the-public service, The Center for Wellness uses an independent third-party system, ActiveNet, for any billing needs.

Patients will be encouraged to participate in up to three in-person or phone visits with the health coach at the beginning, middle, and end of the active 90-day implementation period, with the first visit lasting between 60 and 90 minutes and the other two lasting between 20 and 45 minutes. The health coach will also function as the moderator of the discussion group, as the peer mentor does in the peer-supported group.

Patients will have the option to share selected Tula data with the health coach through a dashboard. When a patient in this group completes a survey, they will be presented with a question: "Do you want to share your responses with the health coach? Yes/No." If the subject responds "yes," their survey responses will populate a dashboard that contains data on drinking days / drinks per day and other data reported via the weekly survey. The health coach will have the option to view the data in the dashboard. Data in the dashboard will not be placed in the patient subject's electronic medical record. However, if the health coach sees any data that is concerning that would normally prompt follow-up within the scope of their clinical role, the health coach will contact and follow-up with the patient subject if such a situation were to arise.

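### Two secondary aims seek the effect of clinician monitoring, but no randomized contrast separates monitoring from the rest of the coach-led package

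*Combined protocol and SAP*

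**What the plan says.** The statement of purpose that opens the protocol says "The study is designed to isolate and examine the role of the clinician in delivering an mHealth system". Section 2.0 lists two secondary aims on monitoring: "Understand the significance clinician monitoring has on alcohol use interventions and patient outcomes" and "Understand the impact clinician monitoring has on AUD treatment".

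Section 1.0 describes what the arms share and where they differ. All participants "download Tula on their smartphones and receive the same static content". It then says "The content of Tula will vary by randomization group in two ways": the communication services available in the app, and whether the participant works with a health coach. In the self-monitoring arm, "participants will not have access to a discussion group with others using the app".

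Section 5.0 gives the detail. For the peer-supported arm, "The only involvement of someone other than patients themselves in the peer-supported Tula group will be by a trained peer mentor"; the mentor moderates the discussion group and cannot see individual use data. In the clinically integrated arm a health coach moderates the group, offers up to three visits and follows up by private message. Patients choose whether to share survey responses to a dashboard, and "The health coach will have the option to view the data in the dashboard".

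Section 7.0 allocates the three arms 1:1:1. Section 8.0 plans pairwise comparisons between arms, a mediation analysis through three psychological needs, and a cost-effectiveness ratio comparing the clinically integrated with the peer-supported arm.

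**The concern.** To isolate an element by randomization, two arms must differ in that element and in nothing else that could affect the outcome. The monitoring aims name one activity, a clinician looking at patient-reported data. The arm that contains it also contains a good deal of coaching contact and a different moderator.

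If the clinically integrated arm does better than the peer-supported arm, the cause could be the visits, the regular messages, the action planning, the change of moderator or the dashboard. If the arms do not differ, useful monitoring may have been offset by the absence of the trained peer mentor, or monitoring may hardly have taken place. Neither result answers the two aims as written. The stake is how the result will be read: the same contrast feeds the cost-effectiveness ratio, and the trial also plans a reimbursement prototype for the clinically integrated arm. A conclusion about monitoring could be carried into implementation decisions without support from the design.

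**Working it through.** The plan gives no figure on this point, so the check is a side-by-side reading of the arms, taken from Sections 1.0 and 5.0.

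| Element | Self-monitoring | Peer-supported | Clinically integrated |
|---|---|---|---|
| Static app content and surveys | yes | yes | yes |
| Discussion group and messages between members | no | yes | yes |
| Moderator and message contact | research coordinator, messages only | peer specialist | health coach |
| Coaching visits | none described | none described | up to three |
| Regular message follow-up by the support person | none described | none described | weekly or bi-weekly |
| Coach-led goal setting and action plan | none described | none described | yes |
| Data shown to the support person | no | no | optional to share, optional to view |

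Counting the rows that differ in each pairwise contrast:

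1. Peer-supported versus self-monitoring: two (group with member messaging; moderator and contact). Neither involves a clinician.
2. Clinically integrated versus peer-supported: five (contact person, visits, message follow-up, planning, dashboard). One of the five is monitoring.
3. Clinically integrated versus self-monitoring: the same five plus the discussion group with member messaging, so six. One of the six is monitoring.

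No contrast differs in the last row alone.

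The added contact is not trivial. Section 5.0 sets the first visit at 60 to 90 minutes and the other two at 20 to 45 minutes each. A patient who attends all three receives between 60 + 20 + 20 = 100 and 90 + 45 + 45 = 180 minutes of coaching, before any messages. Attendance is encouraged and not required, so actual contact may be lower.

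Exposure to monitoring is less certain. Patients are asked at each survey whether to share, and can later withdraw sharing retrospectively. The coach may or may not open the dashboard. Section 5.0 says the coach will follow up concerning data within the clinical role, but that no response is expected in the research role.

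Section 8.0 does not fill the gap. The pairwise comparisons are the three above. The mediators are competence, relatedness and autonomous motivation. The dose/response aim concerns Tula use. The complier-average analysis does not define compliance in terms of monitoring. Table 1 does record how many participants opt to share and, from server logs, how many days clinicians used the report; I take the latter to mean the coach's dashboard. Both are behaviours that follow randomization and occur in one arm only. A comparison of sharers with non-sharers would therefore mix any effect of monitoring with the reasons people chose to share.

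**The case against.** The strongest reply is that the purpose statement speaks of the clinician's role in delivery and does not mention monitoring. On that reading, visits, messages, moderation and dashboard review are the role itself and do not confound it. The static content, a discussion group and member messaging are present in both active arms, so the contrast between them is a sensible one. The protocol also calls the trial a comparison of implementation strategies and openly says that the arms vary in two ways. The monitoring aims are secondary, are phrased as seeking understanding, and have no power calculation attached. Optional sharing is natural in a pragmatic trial, which tests the offer of monitoring.

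Much of this stands. The package contrast is valid, and optional use is no defect in itself. Two things remain. First, even for the role as a whole, the coach is substituted for the peer specialist and not added to that support, so *isolate* is too strong. Second, the Section 2.0 aims name monitoring, and reading the role broadly does not help them.

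A reader might also infer three stronger points that the documents do not support:

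- That the clinically integrated arm loses peer support. It keeps its own discussion group and member messaging; only the trained peer mentor is absent.
- That losing the mentor and changing the moderator are two separate differences. The mentor is the moderator, so this is one swap. Private messaging with the support person also exists in both active arms; what is added is regular follow-up.
- That the plan commits to estimating a monitoring effect, or fails to record monitoring. Section 8.0 specifies no such estimate, and Table 1 already records sharing and report use.

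**Conclusion.** The point holds as one of wording and interpretation for the secondary aims. Five elements change together between the peer-supported and clinically integrated arms, and one of them is monitoring. That contrast supports a conclusion about a coach-led package against a peer-led package. It supports no conclusion, positive or null, about monitoring on its own, and the comparison with self-monitoring does not help because it adds a sixth difference.

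A reader might go further and infer that the main comparison is confounded. It is not: the primary aim asks whether the three groups differ in risky drinking and quality of life, and randomization answers that for the packages as delivered.

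The conclusion assumes that the arms are delivered as Sections 1.0 and 5.0 describe. The entries marked as none described mean that the protocol mentions no such element for that arm. The exact count depends on how coach activities are grouped, but any grouping that distinguishes coaching contact from data review leaves them varying together.

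**What to change.** 1. In the statement of purpose, replace the claim to isolate the clinician's role with wording that the study compares coach-led (clinically integrated) with peer-led delivery of the mHealth system.
2. In Section 2.0, restate the two monitoring aims as that package comparison, with each package also compared with self-monitoring. The two overlap and could be merged.
3. In Section 8.0, state that the counts of data sharing and the report-use logs in Table 1 arise after randomization within one arm, so that any analysis of them is descriptive or exploratory and does not estimate a randomized effect of monitoring.

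This needs no new arm, participants, data or change to the primary analysis. The cost is a protocol wording amendment and a narrower secondary claim. If the effect of monitoring itself is wanted, it would need a design in which monitoring alone varies.
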